##### **6.1.2.2 SPR Trial Stage Success**

Trial Stage success for each subject is the binary outcome pertaining to success (a 2-point or greater decrease in BPI3 during the Trial Stage or failure (a decrease of less than two points, no change in BPI3, or increase of BPI3 during the Trial Stage). BPI3 at the end of the Trial Stage (Visit 5) will be compared to BPI3 at the End of Sham (Visit 4) for subjects who demonstrate either no placebo or a positive placebo effect. For subjects in whom a negative placebo effect was observed, BPI3 results at Visit 5 will be compared against Baseline (Visit 1).

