Primary Clinical Endpoint	
 
• Trial Stage Success 
 
◦ Statistically significant proportion of subjects achieving at least a 2-point reduction in post-stroke shoulder pain intensity score in the BPI Pain Intensity Question #3 (BPI3) at the end of the Trial Stage (Visit 5) relative to end of the placebo period or baseline (Visit 4 or Visit 1), whichever is lower OR reporting a BPI3 score of zero at the end of the Trial Stage.
 
 
 
• Implant Stage Success 
 
◦ Statistically significant proportion of subjects participating in the Implant Stage achieving at least a 2-point reduction in post-stroke shoulder pain intensity score in the BPI Pain Intensity Question #3 (BPI3) at the 12-week post-IPG stim on visit (Visit 10) relative to end of the placebo period or baseline (Visit 4 or Visit 1), whichever
 
 
 

	is lower OR reporting a BPI3 score of zero at the 12-week post-IPG stim on visit.
Secondary Endpoints	
 
• Pain 
 
◦ BPI Pain Interference Question (BPI9)
 
◦ Pain-free passive range of motion
 
 
 
• Quality of Life 
 
◦ Medical Outcomes Study Short Form (SF-36v2)
 
 
 
• Global impact of stimulation therapy 
 
◦ Patient Global Impression of Change (PGIC) scale
 
 
 
• Emotional functioning 
 
◦ Beck Depression Inventory Second Edition (BDI-II)
 
 
 
• Device Performance and User Satisfaction of SPR System
 
• Changes in Quantitative Sensory Testing (QST) thresholds
 
• Impact of Therapy on Arm Impairment using the Stroke Upper Limb Capacity Scale (SULCS)
 
• Economic Impact of Shoulder Pain at Baseline
 

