A subject will be considered an Implant Stage success if he/she achieves at least a 2-point reduction in post-stroke shoulder pain intensity score in the BPI Pain Intensity Question #3 (BPI3) at the 12-week post-IPG stim on visit (Visit 10) relative to end of the placebo period or baseline (Visit 4 or Visit 1), whichever is lower OR reports a BPI3 score of zero at the 12-week post-IPG stim on visit.

All Implant Stage subjects will continue to be evaluated through the 36-month IPG Stim ON follow-up interval to determine the safety profile of the SPR Implant System and to evaluate the effect of dosage on treatment effect. Adverse events will be assessed at all follow-up visits.

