The proportion of subjects achieving success in each stage will be calculated. A 2-point reduction in pain intensity is considered to be the minimum clinically important difference (MCID) on a 0-10 pain numeric rating scale (Farrar et al., 2001). Primary efficacy of the Trial Stage therapy will be determined at the end of the Trial Stage. Primary efficacy of the Implant Stage will be determined at the 12-week post-IPG Stim On follow-up visit. A subject will be considered a Trial Stage Success if he/she achieves at least a 2-point reduction in post-stroke shoulder pain intensity score in the BPI Pain Intensity Question #3 (BPI3) at the end of the Trial Stage (Visit 5) relative to end of the placebo period or baseline (Visit 4 or Visit 1), whichever is lower OR reports a BPI3 score of zero at the end of the Trial Stage.

In addition, the average reduction in pain intensity across all subjects during each stage will be analyzed.

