### **5.4.1 Primary Efficacy Endpoint Analysis**

Within subject analyses of the primary endpoint, the BPI3, are performed for each subject throughout the study. First, the BPI3 is collected and analyzed at the end of the sham period during the SPR Trial Stage, to evaluate the placebo effect. Second, the BPI3 is collected at the conclusion of the SPR Trial Stage to determine the proportion of subjects who experienced clinically significant pain relief during the Trial Stage (i.e., Trial Stage Success proportion). Third, the BPI3 is collected during the Trial Stage Follow-up period to assess the return of pain and determine if a subject is eligible to advance to the SPR Implant Stage. Finally, the BPI3 is collected and analyzed during the SPR Implant Stage to determine the success of the SPR Implant System for the individual.

A subject will be considered a Trial Stage Success if he/she achieves at least a 2-point reduction in post-stroke shoulder pain intensity score in the BPI Pain Intensity Question #3 (BPI3) at the end of the Trial Stage (Visit 5) relative to end

of the placebo period or baseline (Visit 4 or Visit 1), whichever is lower OR reports a BPI3 score of zero at the end of the Trial Stage.

A subject will be considered an Implant Stage success if he/she achieves at least a 2-point reduction in post-stroke shoulder pain intensity score in the BPI Pain Intensity Question #3 (BPI3) at the 12-week post-IPG stim on visit (Visit 10) relative to end of the placebo period or baseline (Visit 4 or Visit 1), whichever is lower OR reports a BPI3 score of zero at the 12-week post-IPG stim on visit.

A description of each analysis is presented below and details regarding the statistical methods are presented in Section 6.

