**$P_0$ =BPI pain score at Baseline**

**$P_1$ =BPI pain score at End of Sham**

#### **P2=BPI pain score at End of Trial Stim**

Then, subjects who demonstrate a positive placebo effect (or no placebo effect) will be considered SPR Trial Stage successes if they demonstrate a 2-point or greater decrease in their BPI3 score from the End of Sham to the End of Trial Stim:

$$P_1 - P_2 \geq 2$$

If the BPI3 score at End of Sham (P1) is less than 2 (e.g. the value is 1 or 0), then BPI3 at the End of Trial Stage (P2) must equal 0 to be considered a Trial Stage Success.

Alternatively, subjects who demonstrate a negative placebo effect (as evidenced by an increase in the BPI3 score during the sham period) will be compared to Baseline (Visit 1), rather than End of Sham. It is critical to compare to the Baseline BPI3 score for these subjects, to ensure that they have achieved pain reduction as a result of the stimulation therapy and not as a result of a placebo effect.

For these subjects, they will be considered SPR Trial Stage successes if they demonstrate a 2-point or greater decrease in their BPI3 score from Baseline to the End of Trial Stim:

$$P_0 - P_2 \geq 2$$

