#### 5.4.1.5 Summary of Pain Score Comparisons

Table 9 summarizes the comparisons that are necessary to determine whether or not a placebo effect is present in each subject, if a subject is a Trial Stage Success, if the subject is eligible to advance to the SPR Implant Stage, and if a subject is considered an Implant Stage success.

**Table 9.** Summary of Pain Score Comparisons

Baseline BPI3	End of Sham BPI3*	Result of Comparison of Sham vs. Baseline	Placebo Effect	End of Trial Stage BPI3*	Trial Stage Success Criteria	Criteria to be consented/screened for the Implant Stage	12-weeks IPG Stim ON	Implant Stage Success Criteria
$P_0$	$P_1$	$P_1 < P_0$	Positive placebo effect	$P_2$	$P_1 - P_2 \geq 2$	$P_3 - P_2 \geq 2$ $P_3 \geq 4$	$P_4$	$P_1 - P_4 \geq 2$
$P_0$	$P_1$	$P_1 = P_0$	No placebo	$P_2$	$P_1 - P_2 \geq 2$	$P_3 - P_2 \geq 2$ $P_3 \geq 4$	$P_4$	$P_1 - P_4 \geq 2$

$P_0$	$P_1$	$P_1 > P_0$	Negative placebo effect	$P_2$	$P_0 - P_2 \geq 2$	$P_3 - P_2 \geq 2$ $P_3 \geq 4$	$P_4$	$P_0 - P_4 \geq 2$
-------	-------	-------------	-------------------------	-------	--------------------	------------------------------------	-------	--------------------

\*If the BPI3 score at End of Sham ( $P_1$ ) is less than 2 (e.g. the value is 1 or 0), then BPI3 at the End of Trial Stage ( $P_2$ ) must equal 0 to be considered a Trial Stage success.

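### Sections 6.1.2.2, 6.1.2.3, 5.4.1.4 and the Implant column of Table 9 leave out the zero-score rule that is part of the stated primary endpoints

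*Combined protocol and SAP*

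**What the plan says.** The primary clinical endpoint in the synopsis has two routes to success in each stage. One is a drop of at least 2 points from the lower of Visit 1 and Visit 4. The other is a score of zero: for the Trial Stage, "reporting a BPI3 score of zero at the end of the Trial Stage"; for the Implant Stage, the reference is whichever score "is lower OR reporting a BPI3 score of zero at the 12-week post-IPG stim on visit". Section 4.1 and the opening of Section 5.4.1 repeat both rules, the latter ending the Implant definition with "whichever is lower OR reports a BPI3 score of zero at the 12-week post-IPG stim on visit". Section 4.4.1.1 repeats the Trial Stage rule. Section 5.4.1.2 adds that if the End of Sham score is below 2, the Visit 5 score "must equal 0 to be considered a Trial Stage Success", and the Table 9 footnote says the same.

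Other places differ:

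- Section 6.1.2.2 compares Visit 5 with End of Sham (or with baseline after a negative placebo effect) and scores as "failure (a decrease of less than two points, no change in BPI3, or increase of BPI3 during the Trial Stage".
- Section 6.1.2.3 uses the same success and failure wording for the Implant Stage.
- Section 5.4.1.4 and the Implant column of Table 9 give only the 2-point rule.
- Section 4.5.2.8 (Visit 5) compares with End of Sham and calls any subject short of 2 points a Trial Stage failure.
- Section 6.1.2 starts the analysis once all implanted subjects have completed Visit 10, then says the efficacy data come from Visit 12.

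**The concern.** Section 6 does more than abbreviate the endpoint. It names a drop of less than 2 points, and no change, as failures. A subject who goes from 1 to 0, or stays at 0, therefore has two opposite classifications in writing.

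The Section 6 outcome feeds the significance test, the 95% confidence interval and the logistic regression in Section 6.1.2.4, and Section 6.2 carries the same analysis to the final report. If the conflict is settled only after data have been seen, the primary outcome becomes a post-hoc choice.

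The Trial Stage conflict also reaches disposition. A subject who succeeds only by the zero rule is a failure under Section 4.5.2.8 and is terminated under Section 4.5.2.9. Under Sections 5.4.1 and 4.5.2.10 the same subject receives monthly follow-up calls and may become eligible for the implant.

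**Working it through.** **Passages side by side**

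| Place | Zero rule, Trial Stage | Zero rule, Implant Stage |
|---|---|---|
| Synopsis; 4.1; 5.4.1 opening | present | present |
| 4.4.1.1; 5.4.1.2 | present | not addressed |
| Table 9 | present (footnote) | absent |
| 5.4.1.4 | not addressed | absent |
| 4.5.2.8 | absent | not addressed |
| 6.1.2.2 | absent; smaller drops named as failure | not addressed |
| 6.1.2.3 | not addressed | absent; smaller drops named as failure |

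The Table 9 footnote does not rescue the Implant column. It concerns only the End of Trial Stage score, which "must equal 0 to be considered a Trial Stage success".

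**Inputs.** P0 is baseline, 4 to 10 (eligibility requires at least 4). P1 is End of Sham, P2 is Visit 5 and P4 is Visit 10, each 0 to 10. Stage sizes are 45 and about 18. The power calculation and the comparison rate are redacted, so there is no stated figure to reproduce.

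**Trial Stage**

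- Stated endpoint: min(P0, P1) − P2 ≥ 2, or P2 = 0.
- Section 6.1.2.2: min(P0, P1) − P2 ≥ 2 only.
- They can differ only if P2 = 0 and min(P0, P1) < 2. Since P0 ≥ 4, this requires P1 = 0 or 1.
- Score patterns: 7 × 11 × 11 = 847. Discordant: 7 baselines × 2 = 14, all success under the endpoint and failure under 6.1.2.2.
- Section 5.4.1.2, with its clause for P1 < 2 read as sufficient for success, agrees with the endpoint in all 847.

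These are counts of possible patterns, not frequencies.

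**Implant Stage.** Entry requires Trial Stage success (Table 2) and a sustained return of pain to at least 4, at least 2 points above P2 (Section 5.4.1.3). For a given P0, the stated endpoint allows 2 + P0(P0 − 1)/2 + (10 − P0)(P0 − 1) successful (P1, P2) pairs. For P0 = 4 to 10 this gives 26 + 32 + 37 + 41 + 44 + 46 + 47 = 273. In all of them P2 ≤ 8, so a return of pain is possible.

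- Trial Stage success by the stated endpoint: 273 × 11 = 3003 patterns, of which 14 are discordant, all with P1 of 0 or 1, P2 = 0 and P4 = 0.
- Trial Stage success by 4.5.2.8 or 6.1.2.2: (273 − 14) × 11 = 259 × 11 = 2849 patterns, none discordant, because no such subject enters.

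The Implant conflict is thus nested in the Trial one. A subject with P1 of 0 or 1 enters only through the zero rule and then cannot succeed under 5.4.1.4 or 6.1.2.3, even if pain-free at Visit 10.

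**Size per subject.** 1/45 = 2.2 points; 1/18 = 5.6 points. If the interval is Clopper-Pearson (an assumption), one success moves the 95% lower limit by 2.04 to 2.74 points for n = 45 with 22 to 40 successes, and by 4.49 to 6.71 points for n = 18 with 9 to 16 successes.

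**Visit number.** Visit 12 is the 9-month visit (Section 4.5.3.10). The synopsis and Sections 4.1, 4.5.3.8, 5.4.1, 5.4.1.4 and 6.1.2.3 place Implant Stage success at 12 weeks or Visit 10. The later analyses in Section 6.1.2 are at 6, 12 and 24 months. Nine months is about 39 weeks, so the subject whose Visit 10 completes the trigger would be about 39 − 12 = 27 weeks short of Visit 12.

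**The case against.** The strongest reply is that the governing definition is explicit. Section 5.4.1 states the zero rule for both stages just above 5.4.1.4 and Table 9, and refers to Section 6 for statistical methods, not for a new endpoint. On that view Sections 6.1.2.2 and 6.1.2.3 are short restatements and the intent is clear. Intent can be inferred, but Section 6 states the opposite classification outright, so the wording still needs correcting.

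The affected group is narrow, especially in the Implant Stage. It takes near-complete relief during sham, zero at Visit 5, a sustained return to at least 4, implantation, and zero again at Visit 10. That stands, and it limits the size of the point. The plan did foresee the case, since it wrote a special clause for End of Sham scores below 2.

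Visit 12 is probably a slip for the 12-week visit. That is likely; it is still the visit number written in the analysis section. Nine-month data are used elsewhere (Sections 4.4.1.1 and 5.4.3), so the criticism is confined to Section 6.1.2.

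The synopsis Study Plan, Section 3.1, the follow-up-call sentence in Section 4.1 and Table 4 mention a 2-point reduction without a reference visit. These are ambiguous, not contradictory. Read against baseline, none of the 77 patterns with a Visit 5 score of 0 fails, because baseline is at least 4.

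**Conclusion.** The concern holds. Programming Section 6.1.2.2, 6.1.2.3 or 5.4.1.4 as written turns some primary-endpoint successes into failures, and never the reverse. Only subjects with an End of Sham score of 0 or 1 who later score 0 are affected. For the Implant Stage, the conflict arises only if such subjects are accepted as Trial Stage successes. The per-subject shifts of 2.2 and 5.6 points assume the planned stage sizes. The documents do not give the number affected, so nothing is claimed about the study's conclusion. The Visit 12 reference is a separate error and conflicts with the trigger stated in the same section.

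**What to change.** For the efficacy analysis, add the zero-score rule to Sections 6.1.2.2, 6.1.2.3 and 5.4.1.4 and to the Implant column of Table 9, so that all match the endpoint in the synopsis and Section 5.4.1. In Section 6.1.2, change Visit 12 to Visit 10.

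For disposition, the sponsor must reconcile Section 4.5.2.8, and with it the termination step in 4.5.2.9, with the success definition in 5.4.1 and the follow-up calls in 4.5.2.10. For clarity, the reference visit can be stated in the synopsis Study Plan, Section 3.1, the follow-up-call sentence in 4.1 and Table 4.

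Optionally, report how many successes rest only on the zero rule, with the success rate and 95% confidence interval with and without them.

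The cost is wording changes, plus one table row if the optional report is added. The changes should be made before the analysis is run.

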##### **6.1.2.3 SPR Implant Stage Success**

Implant Stage success for each subject is the binary outcome pertaining to success (a 2-point or greater decrease in BPI3) or failure (a decrease of less than two points, no change in BPI3, or increase of BPI3) during the Implant Stage of the study. This endpoint will be compared between 12-weeks IPG Stim ON (Visit

10) and the End of Sham (Visit 4) for subjects who demonstrate either no placebo or a positive placebo effect. For subjects in whom a negative placebo effect was observed, results will be compared against Baseline (Visit 1).

#### **6.1.2.4 Overall study success**

Overall study success is defined by the success rate across all subjects participating in each stage, and is expected to exceed the historically observed success rate █ based upon previous and ongoing studies that demonstrated a █ success rate among subjects treated with stimulation therapy (Yu et al., 2001a; Chae et al, 2005; Chae et al., 2013; Wilson et al., 2014; as well as the present study and an unpublished randomized controlled trial).

A test of significance will be carried out to test the null hypothesis that the success rate █ or less versus the alternative that the true success rate exceeds █. In addition, a 95% confidence interval for the true success rate will be reported with the expectation that the lower limit of the interval will exceed █

All treatment failures, including any subjects who had an Implant Stage system removed due to an adverse event, will also be analyzed as part of this analysis.

Finally, a logistic regression will be reported, treating subject success as the binary outcome and baseline BPI as a possible explanatory variable. Other subject characteristics, such as time post-stroke, cortical vs. subcortical, right vs. left affected shoulder, and subluxation versus non-subluxation will be examined via a covariate analysis.

Secondary endpoints will be assessed using non-parametric tests. The Wilcoxon signed-rank test will be used to examine the difference of each endpoint for each subject. We will also investigate the mean improvement by reporting the results using a one-sample t-test.

This interim analysis will also include an examination of mean changes in the normalized dose of nonopioid medications using pain medication data collected at baseline from the subject (including type, dosage, frequency, and whether the medication is used to treat shoulder pain or other types of pain) compared against each subsequent visit. The analysis will be used to confirm that pain medication dosages did not increase for the week prior to each visit and call and during the Trial Stage follow-up period, in accordance with the study protocol. Although subjects will be asked to maintain pain medication dosages, an increase in dosage for breakthrough pain is permitted. For this pilot study, there is no limit on the number of pain medication uses for breakthrough shoulder pain or other types of pain. The number of uses of breakthrough medication will be analyzed for each subject. Further analysis of this data will be used to evaluate the need for limits on rescue medications for breakthrough pain during the future pivotal study on the implantable system.

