***Percutaneous [REDACTED] electrical stimulation***

Percutaneous [REDACTED] electrical stimulation for the treatment of post-stroke shoulder pain was first studied at Case Western Reserve University by Chae and associates. A case report of a chronic stroke patient suffering from shoulder subluxation and pain, who was unable to tolerate surface electrical stimulation, suggested initial clinical feasibility of percutaneous electrical stimulation (Chae et al., 2001). The authors then conducted a pilot study in which eight chronic stroke survivors received six weeks of percutaneous electrical stimulation [REDACTED] [REDACTED]. Subjects experienced a significant improvement in subluxation and self-reported pain (Yu et al., 2001a). This case series was duplicated in the Netherlands with similar reduction in shoulder pain (Renzenbrink and IJzerman, 2004); however, the study also demonstrated significant improvement in pain related quality of life based on the pain domain of the Medical Outcomes Study Short Form (SF-36).

The authors then conducted a double-blind crossover trial to determine whether sensation associated with percutaneous [REDACTED] electrical stimulation is less painful than sensation associated with surface electrical stimulation (Yu et al., 2001b). Subjects rated the pain of each treatment modality using a VAS and the Pain Rating Index of the McGill Pain Questionnaire (Melzach, 1975). The median scores on the VAS and the Pain Rating Index were lower for percutaneous electrical stimulation than for surface electrical stimulation ( $p=0.007$  and  $p=0.018$ , respectively), indicating less pain with percutaneous electrical stimulation. In addition, nine out of ten subjects stated that they would prefer to receive percutaneous electrical stimulation over surface electrical stimulation.

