Yu, Chae, and associates then went on to enroll 61 subjects into a single-blinded randomized controlled study to assess the effect of percutaneous [REDACTED] stimulation on shoulder pain and a variety of secondary endpoints (Yu et al., 2004; Chae et al., 2005). Treatment subjects received 6 hours of stimulation per day for 6 weeks while control subjects received a cuff type sling. Subjects were asked to rate their worst shoulder pain in the last week on an 11 point scale (Brief Pain Inventory short form, question 3) (Cleeland and Ryan, 1994) at various times throughout the 12 month follow-up. The group receiving electrical stimulation showed a significantly higher success rate (as measured by a minimum 2-point

reduction on the scale) than the control group (84% vs. 31%, p=.001 at the end of treatment). The authors concluded that percutaneous [REDACTED] electrical stimulation is safe and effective in reducing shoulder pain.

The need for a long-term therapy solution for post-stroke shoulder pain in a subset of stroke survivors is supported by a post-hoc analysis of the above study results (Chae et al., 2007). A logistic regression analysis of the study results was conducted post hoc to identify predictors of treatment success. The factor most predictive of treatment success was time from stroke onset. Specifically, subjects treated earlier ( $35.4 \pm 16.4$  weeks) post-stroke experienced a significant reduction in shoulder pain at the end of treatment and pain relief was maintained through 12-months post-treatment. Subjects treated later since their onset of stroke ( $211.4 \pm 191.3$  weeks) also achieved significant pain reduction at the end of treatment, but this pain reduction for these subjects dissipated with time after the therapy was turned off. [REDACTED]

[REDACTED] This post-hoc analysis concluded that future trials should consider investigating a permanently implanted device to treat the large prevalent stroke population that falls into the later group.

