#### **4.3.2 Justification of Treatment Duration**

Our study design includes a 6-week SPR Trial Stage with 3-weeks of Sham Stimulation and 3-weeks of Trial Stage Stimulation. Previous [REDACTED] studies (Chae et al, 2005, Yu et al, 2004) used 6-weeks of stimulation, however further analysis of this data showed that the majority of pain reduction for the treatment subjects occurred during the first three weeks of stimulation. We anticipate that 3-weeks of SPR Trial Stage stimulation will be sufficient to determine which subjects will benefit from long-term therapy with the SPR System. Similarly, we anticipate that 3-weeks of sham stimulation will be sufficient to give us an indication of whether subjects experience a placebo effect from having the SPR Trial Stage System present. [REDACTED]

If a subject reports pain relief during the SPR Trial Stage but experiences the specified return of pain, he or she will advance to the SPR Implant Stage. As described above, a post-hoc analysis of the previous randomized controlled trial on [REDACTED] stimulation (Chae et al, 2005), demonstrated that stroke survivors who are treated later after stroke onset responded to a 6-week stimulation therapy but had a return of pain once the therapy was concluded. However, some stroke survivors who are treated soon after stroke onset may experience benefit from a temporary therapy for at least 12-months. Therefore, we are proposing that pain must return in order to warrant a fully implantable system.

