#### 4.7 Study Duration

The duration of the study is expected to be up to 10 years. The study will be conducted at up to five sites enrolling a total of 45 SPR Trial Stage subjects to yield approximately 18 subjects in the SPR Implant Stage. Study enrollment of 45 SPR Trial Stage subjects is expected to take approximately 7 years, and subject participation for those who progress to the SPR Implant Stage can last approximately 3 years.

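### Section 6.1.2.4 compares each stage's success rate with history on unlike scales: this trial's reference score is stricter and, in the Trial Stage, its stimulation is shorter

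*Combined protocol and SAP*

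**What the plan says.** Section 6.1.2.4 judges the success rate in each stage, which "is expected to exceed the historically observed success rate". It adds: "A test of significance will be carried out to test the null hypothesis that the success rate" is at or below a value that is blacked out, and "a 95% confidence interval for the true success rate will be reported with the expectation that the lower limit of the interval will exceed" another blacked-out value. The sources listed for the historical rate are four published studies, the present study and an unpublished randomised trial. Section 4.3.1 confirms that data collected so far in this trial are in the pool.

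In Sections 4.1 and 5.4.1, success in either stage is a fall of at least 2 points on BPI3 from the lower of the Visit 1 (baseline) and Visit 4 (end of sham) scores, or a score of zero. The Trial Stage is scored at Visit 5, after 3 weeks of active stimulation. The Implant Stage is scored at Visit 10, after 12 weeks.

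Section 2.2.3 describes two of the pooled studies. In the pilot, "eight chronic stroke survivors received six weeks of percutaneous electrical stimulation". In the multicentre randomised trial, "Treatment subjects received 6 hours of stimulation per day for 6 weeks while control subjects received a cuff type sling"; success was a fall of at least 2 points, with 84% on stimulation against 31% on control. No sham run-in is described for either. Section 4.3.2 supports the 3-week period because "further analysis of this data showed that the majority of pain reduction for the treatment subjects occurred during the first three weeks"; it gives no figure and does not discuss the reference score.

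**The concern.** A one-sample comparison with history is meaningful only if both rates count the same event. A rate counted from baseline includes placebo response, regression to the mean and natural course. The 31% success in the sling group shows that many subjects can meet a 2-point threshold without stimulation. This trial's rule is built to remove any fall seen during sham. Setting the stripped rate against an unstripped one makes the device look worse than the earlier systems for reasons of definition.

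Section 1.5 says the study will inform a larger pivotal trial. An unexplained shortfall against history could be misread as weakness of the single-lead approach.

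**Working it through.** **1. The plan's own figure.** The plan is "enrolling a total of 45 SPR Trial Stage subjects to yield approximately 18 subjects in the SPR Implant Stage". The null rate, alternative rate, alpha and power are redacted, so 45 cannot be reproduced. Null rates and alpha below are assumptions.

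**2. Direction.** Let P0, P1 and P2 be BPI3 at Visits 1, 4 and 5.

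- Trial rule: min(P0, P1) − P2 ≥ 2, or P2 = 0.
- Baseline rule: P0 − P2 ≥ 2.

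Because min(P0, P1) ≤ P0, the first branch of the trial rule implies the baseline rule. Entry requires P0 ≥ 4, so P2 = 0 gives P0 − P2 ≥ 4. Every success by the trial rule is therefore a success from baseline.

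Counting integer scores confirms this. For each P0 from 4 to 10 there are P0 − 1 values of P2 that succeed from baseline: 3 + 4 + … + 9 = 42, times 11 values of P1 = 462 triples. Those lost under the trial rule number (P0 − 1)(P0 − 2)/2 (from P1 between 2 and P0 − 1) plus 2(P0 − 2) (from P1 of 0 or 1): 7 + 12 + 18 + 25 + 33 + 42 + 52 = 189. None is gained. These are unweighted counts, not probabilities. The same argument holds for P4 at Visit 10.

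**3. Size of the reference-score effect, under assumptions.** Two simulations apply both rules to the same subjects and the same Visit 5 score.

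- Model A: true pain mean 6.5, SD 1.5; visit noise SD 1.5; entry score at least 4; the sham fall persists; stimulation adds a fall of 2 or 3 points.
- Model B: baseline mean 7.5, SD 1.8, cut to 4–10; fall to Visit 5 with mean 4.3, SD 2.8 or mean 4.0, SD 2.5, chosen to give about 84% from baseline; sham change SD 1.5, independent of response.

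| Model | Mean sham fall | From baseline, % | Trial rule, % | Loss, points |
|---|---|---|---|---|
| A (2 / 3) | 0 | 62.0 / 78.8 | 45.3 / 65.6 | 16.7 / 13.2 |
| A (2 / 3) | 1 | 78.9 / 90.2 | 53.6 / 72.6 | 25.3 / 17.6 |
| A (2 / 3) | 2 | 90.2 / 96.3 | 58.8 / 76.7 | 31.4 / 19.6 |
| B (4.3 / 4.0) | 0 | 84.2 / 84.0 | 77.6 / 76.6 | 6.6 / 7.4 |
| B (4.3 / 4.0) | 1 | 84.1 / 84.0 | 70.3 / 68.3 | 13.8 / 15.7 |
| B (4.3 / 4.0) | 2 | 84.1 / 84.1 | 60.3 / 57.2 | 23.8 / 26.9 |

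The range is 6.6 to 31.4 points. With visit noise SD 1.0, model A gives about 9 to 32. There is a loss even with no mean sham change, because the lower of two noisy scores is taken.

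**4. Duration, Trial Stage only.** In model B, if only 80% of the effect is reached by week 3, the baseline-referenced rate falls from 84% to 80–81%; at 60% it falls to 73–74%. With a 1-point sham fall as well, the trial-rule rate is 59–62% (80% share) or 45–49% (60% share). The documents give no value for this share.

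**5. Consequence for the test.** Exact binomial, n = 45, one-sided alpha 0.025 (assumed). The comparison is 84% from baseline against 70% by the trial rule (model B, 1-point sham fall, full effect by week 3).

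| Assumed null | Successes needed | Pass probability at 84% | Pass probability at 70% |
|---|---|---|---|
| 50% | 30 | >0.99 | 0.75 |
| 60% | 34 | 0.95 | 0.26 |
| 70% | 38 | 0.57 | 0.02 |
| 84% | 43 | 0.018 | <0.001 |

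**The case against.** A reader might infer that an equally effective device would fail. The documents do not support that. The null is redacted and may lie below the pooled rate; a low null could absorb much of the bias, as the 50% row shows. If the null equals the pooled rate, an equally effective device passes with probability at most alpha even when definitions match (0.018 at 84%), so the mismatch would not be the main cause of failure.

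A reader might also take the whole benchmark to be 6-week results counted from baseline. Six weeks is documented for two of the six sources. Counting from baseline is inferred from the absence of a described run-in. One source is this trial, presumably scored by its own rule. That dilutes the mismatch and adds circularity.

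The duration point does not carry over to the Implant Stage, which is judged at 12 weeks. That stage also admits only Trial Stage successes whose pain returned, a selection that may push its rate the other way. Only the effect of the reference score is established there, not the net direction.

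The strict reference is deliberate: Section 5.4.1.2 explains it as guarding against placebo response. That is a sound reason for the primary endpoint. It does not make the resulting rate comparable with studies that had no such guard.

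Finally, every simulation input is assumed, and a positive correlation between sham response and stimulation response would shrink the loss. Section 4.3.2 also suggests that the duration loss may be modest. These points limit the size of the effect. They do not remove the difference in scale.

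**Conclusion.** The point holds as one of comparability. For the same scores, this trial's rule gives an equal or lower success rate than a fall from baseline; this follows from the definitions and the entry score of at least 4. In the Trial Stage, shorter stimulation than in the two studies with a stated duration probably lowers the rate further. No visible text adjusts the benchmark for either difference.

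The size cannot be determined from the documents. The range of 6.6 to 31.4 points for the reference score is illustrative and rests wholly on assumed inputs. Whether the bias would change the study's conclusion depends on the redacted null. The sham-referenced endpoint itself is not at fault.

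**What to change.** - Keep the sham-referenced rate as the primary endpoint.
- For the comparison with history, also report the baseline-referenced rate with its 95% confidence interval: P0 − P2 ≥ 2 for the Trial Stage and P0 − P4 ≥ 2 for the Implant Stage. Base the historical conclusion on that rate. The zero-score clause is not needed here, since entry requires P0 ≥ 4.
- Take the present study's data out of its own benchmark, leaving five sources.
- State for each pooled rate the reference score, the stimulation duration and the time elapsed since baseline. Visit 1 to Visit 5 spans 3 + 3 = 6 weeks, of which 3 are stimulated. It should not be set against a 3-week historical rate as if elapsed time matched, because that would favour the device. Against a 6-week rate, elapsed time matches but stimulation time does not. Say so.

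The cost is SAP wording, one extra proportion per stage from scores already collected, and a re-tabulation of the earlier studies. The downside is that the baseline-referenced rate includes placebo response. It must be labelled as a comparison with history and not as evidence of effect over sham.
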